PROTOCOL TITLE:

VERSION DATE:

PROTOCOL TITLE:

Association between a Pharmacogenetic Algorithm to Predict Blood Pressure Therapy with Blood Pressure Response to Anti-Hypertensive Therapy.

PRINCIPAL INVESTIGATOR or FACULTY ADVISOR:

[name]

Pharmacy

[contact]

[contact]

STUDENT INVESTIGATOR:

N/A

VERSION NUMBER/DATE:

1: 9.22.17

PROTOCOL TITLE:

VERSION DATE:

REVISION HISTORY

Revision #	Version Date	Summary of Changes	Consent Change?

PROTOCOL TITLE:

VERSION DATE:

Table of Contents

After completing your protocol, right click on the Table of Contents below and select “Update Field.” If prompted, select “Update entire table.” This will automatically update the protocol sections and page numbers for you. Do this also each time you modify your protocol after initial approval.

1.0	Objectives	6
2.0	Background	6
3.0	Study Endpoints/Events/Outcomes.....	9
4.0	Study Intervention(s)/Investigational Agent(s).....	9
5.0	Procedures Involved	10
6.0	Data and Specimen Banking.....	13
7.0	Sharing of Results with Participants.....	13
8.0	Study Duration	13
9.0	Study Population	13
10.0	Vulnerable Populations	14
11.0	Local Number of Participants	15
12.0	Local Recruitment Methods	15
13.0	Withdrawal of Participants.....	16
14.0	Risks to Participants.....	16
15.0	Potential Benefits to Participants	16
16.0	Data Management.....	16
17.0	Confidentiality	18
18.0	Provisions to Monitor the Data to Ensure the Safety of Participants	18
19.0	Provisions to Protect the Privacy Interests of Participants	18
20.0	Compensation for Research-Related Injury	19
21.0	Consent Process.....	19
22.0	Setting.....	19
23.0	Multi-Site Research.....	19
24.0	Resources Available	19
25.0	References.....	20

PROTOCOL TITLE:

VERSION DATE:

ABBREVIATIONS/DEFINITIONS

BP/Blood Pressure

PROTOCOL TITLE:

VERSION DATE:

STUDY SUMMARY

Study Title	Association between a Pharmacogenetic Algorithm to Predict Blood Pressure Therapy with Blood Pressure Response to Anti-Hypertensive Therapy.
Study Design	Retrospective Association Study
Primary Objective	To retrospectively assess the effectiveness of the use of a patient's genes to predict which hypertension therapy is successful: 
1. Level of blood pressure control (<140/<90)2. Change in blood pressure from baseline to control
Secondary Objective(s)	
1. Number of medications needed to obtain control2. Time to control3. Number of office visits to control4. Side effects from hypertension therapy5. Hypertension associated adverse events during the course of treatment
Research Intervention(s)/Investigational Agents	Association between blood pressure control and genetic variants important in blood pressure regulation.
IND/IDE # (if applicable)	
Investigational Drug Services # (if applicable)	
Study Population	Hypertensive patients who have achieved BP control
Sample Size (number of participants)	Up to 2000
Study Duration for Individual Participants	Less than one day

PROTOCOL TITLE:

VERSION DATE:

1.0 Objectives

Purpose: To assess the effectiveness of the use of a patient's genes to predict which hypertension therapy is successful, as measured by:

- 1. Level of blood pressure control (<140/<90)**
- 2. Change in blood pressure from baseline to control**
- 3. Number of medications needed to obtain control**
- 4. Time to control**
- 5. Number of office visits to control**
- 6. Side effects from hypertension therapy**
- 7. Hypertension associated adverse events during the course of treatment**

2.0

Background

1. Significance of Research Question/Purpose:

Hypertension is known to have a strong heritable component. Previous work has demonstrated that sons of hypertensive patients are more likely to be hypertensive when compared to sons of normotensive individuals. Additionally, monozygotic twins are more likely to share hypertension than dizygotic twins who are more likely than non-twin siblings to share hypertension. Each of these previous studies demonstrate that genetics plays a role in the development of hypertension. For each major class of drugs (diuretic, vasodilator, and β -blocker) the effectiveness rate ranges from 40-60%. Contrary to common belief, even a small ~10-20% of patients have an increase in blood pressure with a given anti-hypertensive medication. These effectiveness rates go far beyond adherence in that these previous trials have controlled for medication adherence. In addition to this controlled studies, epidemiologic data has demonstrated that 40% of patients who take their medication, as prescribed by their clinician, do not have their blood pressure under control.

Unfortunately, despite a significant impulse in the medical community to move towards an "individualized medicine" approach to patient centered treatment, the current clinical treatment strategy is based on a set algorithm which does not take into account individual patient differences. Rather, physicians are guided to choose a drug (one out of many options) in a given class of drugs and use that specific drug as a "first line therapy" (typically initiating with the diuretic class) and titrate that specific drug of choice to therapeutic dosage regardless of efficacy². It is only after a prolonged course of treatment with that specific class of drug that clinical efficacy is determined (typically three months). At this stage, if clinical guideline goals for blood pressure have not been met, it is often recommended that the patient remain on the "first line therapy" whilst an additional drug from a different class of drugs (typically an Angiotensin converting enzyme inhibitor (ACE inhibitor) or Angiotensin II receptor blocker (ARB)) is added to the

PROTOCOL TITLE:**VERSION DATE:**

pharmacologic regimen. Again, this drug is titrated to recommended therapeutic dosage and another prolonged course of treatment is initiated before clinical efficacy is determined (an additional three months – six months since initiation of treatment). If at this point, clinical guideline goals for blood pressure have not been met, a third drug from a third class of drugs (typically a beta-blocker) is added and the process is repeated (another three months – nine months from initiation of treatment). Further, if clinical guideline goals have continued to be elusive, the diagnosis of refractory hypertension is added and the process is reinitiated with a different combination of drugs, different classes of drugs, different drug options within a given class of drugs, different dosages, or all of the above. Thus, from the time of initial diagnosis and the start of treatment to the point in which blood pressure is adequately controlled may take anywhere from three months to well over one year. This trial-and-error standard of care is clearly not optimal.

The blood pressure panel created by Geneticure has been created to comprehensively assess seventeen common genetic variants in the liver (drug metabolizing enzyme) cardiac, vascular, and renal systems that can improve therapeutic guidance for the clinician based on known functional alterations of the protein through these genetic changes, as well as demonstrated effects of certain drug classes on these various genotypes. Based on this information, a clinician can guide therapy with knowledge specific to their patient, rather than “trial-and-error” based on population data and using drugs with least side effects initially.

1. Preliminary Data: N/A
2. Existing Literature:

Background

Hypertension (high blood pressure) is one of the most important preventable contributors to disease and death in the United States and represents the most common condition seen in the primary care setting^{1,2}. According to the American Heart Association, approximately 78 million adults (1 in 3) living in the United States have hypertension with more than 5 million new diagnoses made each year^{3,4}. Of these individuals, 82% are aware they have it, 75% are currently being treated for it, but only 52% have their blood pressure under control (thus, ~48% do not have adequate blood pressure control). Hypertension is known to lead to myocardial infarction, stroke, renal failure, and death if not detected early and treated appropriately. In fact, in 2009, high blood pressure was listed as a primary or contributing cause of death in ~350,000 of the ~2.4 million U.S. deaths (14% of all deaths). From 1999-2009 the number of deaths attributable to hypertension increased by 44%. In 2009, the direct and indirect economic burden on the United States health care system associated with hypertension was

PROTOCOL TITLE:

VERSION DATE:

estimated at \$51 billion. With the advent of improved diagnostic techniques, increased rates of health care utilization and screening, and the increasing age of the population, a continual upward trend in this expenditure is expected. Because nearly two-thirds of the people living with hypertension worldwide reside in developing countries, providing optimal treatment at the lowest cost is critically important.

Hypertension is known to have a strong heritable component. Previous work has demonstrated that sons of hypertensive patients are more likely to be hypertensive when compared to sons of normotensive individuals. Additionally, monozygotic twins are more likely to share hypertension than dizygotic twins who are more likely than non twin siblings to share hypertension. Each of these previous studies demonstrate that genetics plays a role in the development of hypertension. For each major class of drugs (diuretic, vasodilator, and β -blocker) the effectiveness rate ranges from 40-60%. Contrary to common belief, even a small ~10-20% of patients have an increase in blood pressure with a given anti-hypertensive medication. These effectiveness rates go far beyond adherence in that these previous trials have controlled for medication adherence. In addition to this controlled studies, epidemiologic data has demonstrated that 40% of patients who take their medication, as prescribed by their clinician, do not have their blood pressure under control.

Unfortunately, despite a significant impulse in the medical community to move towards an “individualized medicine” approach to patient centered treatment, the current clinical treatment strategy is based on a set algorithm which does not take into account individual patient differences. Rather, physicians are guided to choose a drug (one out of many options) in a given class of drugs and use that specific drug as a “first line therapy” (typically initiating with the diuretic class) and titrate that specific drug of choice to therapeutic dosage regardless of efficacy². It is only after a prolonged course of treatment with that specific class of drug that clinical efficacy is determined (typically three months). At this stage, if clinical guideline goals for blood pressure have not been met, it is often recommended that the patient remain on the “first line therapy” whilst an additional drug from a different class of drugs (typically an Angiotensin converting enzyme inhibitor (ACE inhibitor) or Angiotensin II receptor blocker (ARB)) is added to the pharmacologic regimen. Again, this drug is titrated to recommended therapeutic dosage and another prolonged course of treatment is initiated before clinical efficacy is determined (an additional three months – six months since initiation of treatment). If at this point, clinical guideline goals for blood pressure have not been met, a third drug from a third class of drugs (typically a beta-blocker) is added and the process is repeated (another three months – nine months from initiation of treatment). Further, if clinical guideline goals have continued to be elusive, the diagnosis of refractory hypertension is added and the process is reinitiated with a different combination of drugs, different classes of drugs, different drug options within a given class of drugs, different dosages, or all of the

PROTOCOL TITLE:

VERSION DATE:

above. Thus, from the time of initial diagnosis and the start of treatment to the point in which blood pressure is adequately controlled may take anywhere from three months to well over one year. This trial-and-error standard of care is clearly not optimal.

The blood pressure panel created by Geneticure has been created to comprehensively assess seventeen common genetic variants in the liver (drug metabolizing enzyme) cardiac, vascular, and renal systems that is being studied to see if it can improve therapeutic guidance for the clinician based on known functional alterations of the protein through these genetic changes, as well as demonstrated effects of certain drug classes on these various genotypes. Based on this information, a clinician can guide therapy with knowledge specific to their patient, rather than “trial-and-error” based on population data and using drugs with least side effects initially.

3.0 Study Endpoints/Events/Outcomes

1. Primary Endpoint/Event/Outcome:

To assess the effectiveness of the use of a patient’s genes to predict which hypertension therapy is successful, as measured by:

1. Level of blood pressure control (<140/<90)
2. Change in blood pressure from baseline to control

2. Secondary Endpoint(s)/Event(s)/Outcome(s):

Blood Pressure control with respect to:

1. Number of medications needed to obtain control
2. Time to control
3. Number of office visits to control
4. Side effects from hypertension therapy
5. Hypertension associated adverse events during the course of treatment

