16.0 Data Management

1. Data Analysis Plan:

The Investigator is responsible to ensure the accuracy, completeness, and timeliness of reported data.

PROTOCOL TITLE:

VERSION DATE:

All data will be compiled within the Fairview system on secure servers. De-identified final data may be sent to Geneticure using a secure, password-protected Excel spreadsheet on a server that is only accessible to IRB-approved personnel and is fully auditable. The database will be validated prior to use in the study. All required data will be recorded on CRFs or paper facsimiles. Data collected within the CRFs will be supported by source documents as appropriate and may be updated to reflect the latest observations on the subjects participating in the study. Corrections to the source documentation will be made in a manner that does not obscure the original entry and will be dated and initialed by the Investigator or assigned designee. It is important for data entry to occur in a timely manner, therefore, data collected on source documents should be transferred into CRFs as soon as possible following study visits.

All data will be coded for statistical analysis (i.e. drug classes will be coded numerically and genotypes will be coded numerically). Subject's raw genetic data will be entered into the Geneticure for Hypertension algorithm. All data will be analyzed with SPSS v.20. Normality of the data will be assessed using Levene's test prior to statistical analysis and any correction for non-normal data distribution will be used. Descriptive statistics will be computed (average time for blood pressure control, average number of visits to the clinician for blood pressure control, age, height, weight, BMI, etc.).

Data will be initially analysed following the collection of samples/data from up to 600 subjects. Statistical tests will be corrected for the number of tests run (preservation of alpha). Ordinary least squares regression via univariate modelling will be used to estimate the magnitude of linearity between drug class that yielded the best blood pressure control and genetic profile of the subject. Multiple regression analysis will be performed to determine the impact of confounding variables (height, weight, age, race) on blood pressure control. For all statistical analyses an alpha level of 0.05 will be used to determine statistical significance.

Missing Data

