17 genes that are contained within the Geneticure panel for hypertension treatment. Several of the genes with large effects can demonstrate statistical differences at relatively small sample sizes. For instance position 49 of the beta-1 adrenergic receptor demonstrates a functional genotype mean arterial blood pressure of 97mmHg (SD of 12.4mmHg) with beta-blocker therapy and the non-functional genotype demonstrates a mean arterial blood pressure of 102mmHg (SD of 11.5mmHg) with this same therapy. A power calculation based on this site of the beta-1 adrenergic receptor would yield a sample size per group needed of 109 for an alpha level of 0.05 and a power of 0.80 (not correcting for multiple comparisons) (table 1). Based on these results we can determine that the gene with the smallest effect from this previous smaller study (specifically that encoding WNK-1, rs2107614) will determine the approximate sample size needed to observe an effect, if an effect exists, for the panel as a whole in this prospective trial. Data from our phase-I trial demonstrates a mean arterial blood pressure of 97.6mmHg with diuretic therapy in the functional genotype group of WNK-1 and a mean arterial blood pressure of 100.8mmHg (Pooled SD = 12) with diuretic therapy in the non-functional genotype group for this site of WNK-1. Without correcting for multiple comparisons, one can determine that a per-group sample size of 162 individuals would be needed for 80% power with an alpha of 0.01. Using an alpha of 0.05 and a power of 0.80 we have estimated that we will need 300 subjects per group to observe a significant difference, where one exists. Based on possible retention of 70% of subjects who initially enroll, we will seek to recruit up to 2000 subjects for the study.

Concomitant Medications/Treatment/Procedures

This study protocol does not require change to any existing treatments or those prescribed during the course of the study by the Investigator or any other provider whom the subject sees for any medical reason. Outside of eligibility screening, there are no clinical evaluations planned as part of this study.

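### No single test answers the primary objective: two primary blood pressure measures have no combining rule, the genetic predictor is not fixed, and the stated regression has neither measure as its outcome

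*Combined protocol and SAP*

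**What the plan says.** **Outcome side.** Section 3.0 sets out to use genes to "predict which hypertension therapy is successful, as measured by" two primary measures, "Level of blood pressure control (<140/<90") and "Change in blood pressure from baseline to control", and lists five secondary ones. The Study Summary makes the same split. Section 1.0 lists all seven under one purpose: "To assess the effectiveness of the use of a patient's genes to predict which hypertension therapy is successful, as measured by". None of these places says whether either primary measure suffices or both are needed, and none says whether the change is in systolic, diastolic or mean arterial pressure.

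**Genetic side.** Section 2.0 describes a panel of 17 variants. Section 4.0 lists 18 SNPs in 11 genes, and its itemised counts do add up to 18. The flow of activities in Section 5.0 says 19. The Data Analysis Plan in Section 16.0 enters genotypes into an algorithm and also refers to a genetic profile. The Power Analysis speaks of 17 genes, then takes the smallest single-site effect (WNK-1, rs2107614) to set the sample size "needed to observe an effect, if an effect exists, for the panel as a whole in this prospective trial".

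**Analysis side.** The Data Analysis Plan describes one univariate regression, relating the best-performing drug class to genetic profile. It also describes a multiple regression of blood pressure control on height, weight, age and race, with no genetic term named. On error control it says "Statistical tests will be corrected for the number of tests run (preservation of alpha") and then "For all statistical analyses an alpha level of 0.05 will be used to determine statistical significance".

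**The concern.** A primary objective needs a result, identifiable in advance, that answers it. Here three things are open at once: the measure, the predictor, and the model that joins them. A single SNP significant on one pressure could be presented as the panel predicting therapy. The same data could be presented as negative because the other primary measure, or the panel-level result, was not significant. Nothing in the plan rules out either report.

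The promised correction does not close this gap. It limits how often some test is falsely positive. It does not say which test is the answer, and because it is tied to the number of tests eventually run, the threshold for the primary question depends on how many other questions are asked.

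The first primary measure raises a further difficulty. The Study Summary describes the population as patients who have already reached control, and Section 4.0 requires a history of two consecutive controlled readings. Read as a yes/no outcome, control may hardly vary.

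**Working it through.** **Inputs.** From Section 16.0, Power Analysis: mean arterial pressure 97.6 versus 100.8 mmHg on diuretics by WNK-1 genotype (difference 3.2), pooled SD 12, 300 per group, alpha 0.05, power 0.80. Sidedness is not stated; two-sided is assumed.

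**The plan's own figure.** n per group = 2(z₀.₉₇₅ + z_power)² × SD² / difference².
- Power 0.80: 2 × (1.960 + 0.842)² × 144 / 10.24 = 221.
- Power 0.90: 2 × (1.960 + 1.282)² × 144 / 10.24 = 296.

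So 300 does not reproduce at 0.80; it corresponds to about 90% power for one test. That is a separate matter, but it sets the starting point below.

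**Power for one contrast when m tests share alpha equally.** The standardised effect is 3.2 / (12 × √(2/300)) = 3.266. Power ≈ Φ(3.266 − z), where z is the two-sided critical value at 0.05/m. The last column uses the noncentral t.

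| m | Meaning | 0.05/m | z | Normal | Noncentral t |
|---|---|---|---|---|---|
| 1 | one named test | 0.05 | 1.960 | 0.904 | 0.903 |
| 2 | both primary measures | 0.025 | 2.241 | 0.847 | 0.846 |
| 7 | all listed measures | 0.0071 | 2.690 | 0.718 | 0.714 |
| 36 | 18 SNPs × 2 measures (assumed) | 0.0014 | 3.197 | 0.528 | 0.522 |

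This applies the one published effect to every test, which is an assumption. The plan fixes no row, so the threshold may lie anywhere from 0.05 to about 0.0014.

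**How often the either and both rules give different verdicts.** Take two measures, each with 80% power at 0.05; their correlation is assumed.
- Correlation 0: either = 1 − 0.2² = 96.0%; both = 0.8² = 64.0%; the rules differ in 32.0% of studies.
- Correlation 0.5: 91.3% and 68.7%; they differ in 22.6%.
- Correlation 0.9: 85.0% and 75.0%; they differ in 10.0%.

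With no true effect and no correction, the either rule is positive in 1 − 0.95² = 9.75% of studies and the both rule in 0.25% (7.0% and 3.0% at correlation 0.9). Applying the promised correction to two tests (0.025 each) would hold the either rule to at most 5%.

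**Control as a deciding or gating test.** Simulate the same effect with 300 per group, cutting the same pressure at a threshold that leaves an assumed share controlled. Both tests are significant in about 32% of studies at 95% controlled and about 11% at 99%. A sequence that had to pass through control would usually stop there.

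**Does the stated analysis settle the matter?** No. The univariate regression has drug class and genetic profile as its two sides. The multiple regression has control as its outcome but names no genetic term. The power calculation uses a further quantity, on-treatment mean arterial pressure at one site within one drug class. These three descriptions do not share an outcome and a predictor.

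**The case against.** The strongest reply is that the plan already promises correction for the number of tests. Read with the 0.05 sentence, this most naturally means an overall 0.05. That stands. A reader might infer that the study runs a false-positive risk of 55% or even 84% from 36 uncorrected tests. The documents do not support this: correction is promised, and no section plans 18 SNP tests on each measure. That grid is a construction used here only to show how far the threshold could move.

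A reader might also infer that multiplicity necessarily takes power below the stated 0.80. It does not: two corrected tests at 300 per group still have 85%. The loss needs a larger family or a both rule. Nor is it right that there is no ordering at all, since Section 3.0 and the Study Summary separate primary from secondary measures.

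It is also fair that the title, the algorithm sentence and the phrase genetic profile point towards the panel as the intended predictor, and that Section 16.0 calls the work pilot or feasibility. That argues against elaborate gatekeeping. It does not supply a deciding test: how the algorithm's output becomes a tested variable is nowhere stated, and the protocol still declares a primary objective, an alpha and a power.

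**Conclusion.** The concern holds in this form: the plan does not identify, before the data are seen, which result answers its primary objective. That conclusion rests on the text alone.

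The size depends on what is assumed. The choice between the either and both rules changes the verdict in 10% to 32% of studies if each measure has 80% power and the correlation is between 0.9 and 0. Under an equal split of alpha, power for one contrast is 90%, 85%, 71% or 52% for 1, 2, 7 or 36 tests; the last count is hypothetical. All the power figures borrow the WNK-1 effect on on-treatment mean arterial pressure in diuretic users.

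Control below 140/90 is a poor candidate for the deciding test or for a gate, because the population is described as already controlled. The degree is uncertain: the inclusion criteria in Section 9.0 do not repeat that requirement, so the controlled share is not known from the documents.

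**What to change.** In Sections 3.0 and 16.0:

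- **Name one deciding panel-level test, two-sided at 0.05.** For example, compare change in one stated pressure between subjects whose drug class agrees with the algorithm's output and those whose class does not. This requires that the algorithm yields a drug class, which the protocol does not state, and that baseline pressure is abstracted. Section 5.0 names only the most recent reading, though the attached metrics list, not available here, may cover baseline.
- **Replace the drug-class regression sentence** as the primary analysis with the model for that test, with its covariates.
- **Treat the rest as supportive or exploratory:** blood pressure control, the five secondary outcomes and all single-SNP tests. Correct within each family by a named method, and do not gate any of them through control. Reword the correction and 0.05 sentences to match.
- **State the limit on claims:** no single SNP or secondary result alone supports the statement that the panel predicts therapy.
- **Reconcile the 17, 18 and 19 variant counts**, so that the panel and the SNP family are defined.

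This is mainly a change of wording and needs no extra subjects if the two conditions above are met. The cost is that control and single SNPs can no longer carry the claim alone. The 90% power figure does not automatically transfer to the new test, whose effect size and group sizes are unknown; the power section should say so.
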